5.2 Treatment Details (Cycles 1 & 2)

Intrathecal cytarabine: IT

All patients will receive 1 dose of IT cytarabine using age-based dosing below at the time of diagnostic lumbar puncture, or on Day 0 of each cycle. Patients may be given intrathecal cytarabine up to 1 week prior to Day 1, but at least 24 hours prior to the start of MLN4924 (pevonedistat) and azacitidine on Day 1. If IT cytarabine is given prior to enrollment, a separate institutional consent must be obtained.

Age-based dosing:

Age (yrs)	Dose
< 1	20 mg
1-1.99	30 mg
2-2.99	50 mg
≥ 3	70 mg

Triples (Methotrexate/Hydrocortisone/Cytarabine): IT

For CNS2/3 patients only. IT triples may be given instead of IT cytarabine for CNS2/3 patients in Cycle 1 after the Day 0 IT cytarabine dose per the details described below.

Age-based dosing:

Age (yrs)	Dose
<1	MTX: 7.5 mg, HC: 7.5 mg, ARAC: 15 mg
1-1.99	MTX: 8 mg, HC: 8 mg, ARAC: 16 mg
2-2.99	MTX: 10 mg, HC: 10 mg, ARAC: 20 mg
3-8.99	MTX: 12 mg, HC: 12 mg, ARAC: 24 mg
≥ 9	MTX: 15 mg, HC: 15 mg, ARAC: 30 mg

For CNS2 or CNS3 patients:

Patients with CNS2 or CNS3 involvement at screening will receive additional intrathecal chemotherapy with IT cytarabine or IT triples (doses as above) at a twice weekly schedule until the CNS is clear of blasts on 2 consecutive LPs. The administration of IT cytarabine vs IT triples is up to the treating physician's discretion. A minimum of 4 and a maximum of 6 intrathecal treatments may be given. This count includes the pre-study/Day 0 dose. Subjects who have persistent CNS disease despite 6 doses of IT cytarabine or IT triples will be off study treatment and considered treatment failures (See [Section 12.2.5](#)). See [Section 12.3](#) for definitions of CSF involvement.

Azacitidine: IV over 15 minutes once daily

Days: 1-5

Dose: Age based dosing

Age	Dose
<1 year	2.5 mg/kg/dose
≥ 1 year	75 mg/m ² /dose

Note: infusion must be completed within 1 hour of vial reconstitution

On Days 1, 3, and 5 azacitidine will be given 30-60 minutes before MLN4924 (pevoneditat) infusion. See details of the timing below.

MLN4924 (Pevonedistat)*: IV over 60 minutes

Days: 1, 3, and 5

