Starting dose: 20 mg/m² for patients ≥ 1 year of age; 15 mg/m² for patients < 1 year of age (Dose Level 1). See Dosing Schema in [Section 5.4](#).***NOTE:** Give MLN4924 (pevoneditat) 30 – 60 minutes after the completion of the azacitidine infusion. If MLN4924 (pevoneditat) dosing is delayed, a minimum of 1 full calendar day between any 2 doses should be maintained.**Fludarabine: IV over 30 minutes once daily**

Days: 6-10

Dose: Age based dosing

Age	Dose
< 1 year	1 mg/kg/dose
≥ 1 year	30 mg/m ² /dose

High Dose Cytarabine: IV infusion over 1-3 hours once daily

Days: 6-10

Dose: Age based dosing (begin 4 hours after start of fludarabine)

Age	Dose
< 1 year	67 mg/kg/dose
≥ 1 year	2000 mg/m ² /dose

Please note: Following/during high-dose cytarabine, chemical conjunctivitis may occur. Administer steroid eye drops (0.1% dexamethasone or 1% prednisolone ophthalmic solution), 2 drops to each eye every 6 hours, beginning immediately before the first dose and continuing for 24 hours after the last dose. If patient does not tolerate steroid eye drops, artificial tears may be administered on an every 2-4 hour schedule.

See the Chemotherapy Administration Guidelines (CAG) on the COG website at: https://cogmembers.org/_files/disc/Pharmacy/ChemoAdminGuidelines.pdf for special precautions and suggestions for patient monitoring during the infusion. As applicable, also see the CAG for suggestions on hydration, or hydrate according to institutional guidelines.

5.3**Criteria for Starting Cycle 2**

Patients may proceed to cycle 2 following completion of cycle 1 disease assessment if stable or greater response and if non-hematologic toxicities probably or definitely related to MLN4924 (pevoneditstat) recover to \leq grade 2. Bilirubin, ALT, and AST must be \leq Grade 1 or at the patient's baseline values prior to starting Cycle 2.

NOTE: See [Appendix III](#) for Toxicity Specific Grading.

- Patients will have disease assessment on Day 36-39 of Cycle 1. If a bone marrow aspirate cannot be evaluated (dry tap, no spicules), a follow-up bone marrow aspirate and biopsy must be performed within 2 weeks to assess cellularity and response.
- If aspirate and/or biopsy results indicate hypocellular marrow (<10% cellularity on biopsy), then continue to repeat bone marrow aspirate and/or biopsy not less than once every 14 days until response can be assessed.

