- If count recovery is noted within 14 days of an unevaluable marrow, there is no need to repeat the marrow to confirm response.
- If the patient meets criteria for CR, CRp, or CRi after Cycle 1 then the patient can proceed to Cycle 2 (See [Section 12.2](#) for definitions of response)
- If the bone marrow aspirate and/or biopsy performed after Cycle 1 reveals $\geq 5\%$ but $\leq 25\%$ blasts, then the patient should proceed to Cycle 2 of chemotherapy

5.4**Dosing Schema****5.4.1 Dose Confirmation Schema**

The starting dose will be 20 mg/m² for patients ≥ 1 year of age (Dose Level 1) with dose levels for subsequent groups of patients as follows:

Dose Level	MLN4924 (Pevonedistat) Dose (mg/m ²)
-1	15 mg/m ²
1*	20 mg/m²

* Starting Dose Level

The starting dose will be 15 mg/m² for patients < 1 year of age (Dose Level 1) with dose levels for subsequent groups of patients as follows:

Dose Level	MLN4924 (Pevonedistat) Dose (mg/m ²)
-1	10 mg/m ²
1*	15 mg/m²

* Starting Dose Level

There will be no escalations beyond Dose Level 1 (20 mg/m²), as adult studies examining doses higher than 20 mg/m² observed excess toxicity without any apparent disease benefit and no significant differences in pharmacokinetic parameters to suggest significant increase in efficacy.²⁴

If the maximally tolerated dose (MTD) has been exceeded at the first dose level, then the subsequent cohort of patients will be treated at Dose Level -1. If Dose Level -1 is not well tolerated, further de-escalation will not occur. The study will be closed to accrual.

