10.0 CRITERIA FOR REMOVAL FROM PROTOCOL THERAPY AND OFF STUDY CRITERIA

10.1 Criteria for Removal from Protocol Therapy

- a) Evidence of treatment failure (See [Section 12.2.5](#)).
- b) Adverse Events requiring removal from protocol therapy (See [Section 6](#)).
- c) Refusal of protocol therapy by patient/parent/guardian
- d) Non-compliance that in the opinion of the investigator does not allow for ongoing participation.
- e) Completion of 2 cycles of therapy.
- f) Physician determines it is not in the patient's best interest.
- g) Repeated eligibility laboratory studies (CBC with differential, bilirubin, ALT (SGPT) or serum creatinine) are outside the parameters required for eligibility prior to the start of MLN4924 (pevonodistat) (See [Section 8.1](#)).
- h) Study is terminated by Sponsor.
- i) Pregnancy

Patients who are removed from protocol therapy during Cycle 1 should continue to have the required observations in [Section 8.1](#) until the originally planned end of the cycle or until all adverse events have resolved per [Section 13.4.4](#), whichever happens LATER. The only exception is with documentation of the patient's withdrawal of consent. Patients who are removed from protocol therapy in subsequent cycles should have the necessary observations to ensure adequate clinical care.

Patients who are off protocol therapy are to be followed until they meet the criteria for Off Study (see below). Ongoing adverse events, or adverse events that emerge after the patient is removed from protocol therapy, but within 30 days of the last dose of investigational agent, must be followed and reported via RAVE and CTEP-AERS (if applicable). Follow-up data will be required unless consent is withdrawn.

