12.2.5 Treatment Failure

The definition of treatment failure includes:

- A. An increase in the extent of bone marrow infiltration by leukemic cells (absolute increase of \geq 20% blasts) OR
- B. Development of extramedullary disease (EMD) OR
- C. M2 marrow that does not qualify for PR status OR
- D. An M1 marrow with circulating blasts OR
- E. $>$ 25% blasts in the bone marrow after Cycle 1 of therapy
- F. Subjects who have persistent CNS disease despite 6 doses of IT cytarabine or IT triples

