One copy of this Pharmacodynamic Study Form should be uploaded into RAVE. A second copy should be sent with the samples to the address listed in [Section 8.4.6](#). See [Section 8.4](#) for detailed guidelines for packaging and shipping PD – mRNA Transcript Level samples.

Signature: _____ Date: _____
(site personnel who collected samples)

THIS PROTOCOL IS FOR RESEARCH PURPOSES ONLY, SEE PAGE 1 FOR USAGE POLICY

**APPENDIX VII: PHARMACODYNAMICS (NEDDYLATED PROTEIN ANALYSIS) STUDY
FORM – BONE MARROW SAMPLES**COG Pt ID # _____ Cycle 1, Day 1 Date: _____
Please do not write patient names on this form or on samples.Patient Weight: _____ kg Body Surface Area: _____ m²MLN4924 (Pevonedistat) Dose Level: _____ mg/m² MLN4924 (Pevonedistat) Total Daily Dose: _____ mg

WBC: _____ /µL % Blasts: _____ %

In consenting patients, bone marrow samples (2-3 ml) will be collected in heparinized tubes at the following time points: pre-study, and at the end of Cycle 1 on the same day as bone marrow evaluation.

Record the exact time the sample is drawn.

Blood Sample No.	Time Point	Scheduled Collection Time	Actual Date Sample Collected	Actual Time Sample Collected (24-hr clock)
1	Pre-study	Pre-study	____ / ____ / ____	____ ____ : ____ ____
2	End of Cycle 1	Same day as bone marrow evaluation	____ / ____ / ____	____ ____ : ____ ____

One copy of this Pharmacodynamic Study Form should be uploaded into RAVE. A second copy should be sent with the samples to the address listed in [Section 8.4.6](#). See [Section 8.4](#) for detailed guidelines for packaging and shipping PD – mRNA Transcript Level samples.

Signature: _____ Date: _____
(site personnel who collected samples)

THIS PROTOCOL IS FOR RESEARCH PURPOSES ONLY, SEE PAGE 1 FOR USAGE POLICY

APPENDIX VIII-A: THERAPY DELIVERY MAP FOR CYCLE 1

Therapy Delivery Map – Cycle 1

This Therapy Delivery Map (TDM) relates to Cycle 1. Each cycle lasts 35 days.

Patient COG ID number

DOB

Criteria to start each cycle are in [Section 5.3](#). Extensive treatment details are in [Section 5.2](#).

This TDM is on 4 pages.

DRUG	ROUTE	DOSAGE	DAYS	IMPORTANT NOTES
IT Cytarabine (ARAC) (all patients)	Intrathecal (IT)	Age-based dosing: Age (yrs) Dose < 1 20 mg 1-1.99 30 mg 2-2.99 50 mg ≥ 3 70 mg	0	Given at the time of diagnostic lumbar puncture OR Day 0.

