- m. CSF for cell count, cytospin. Prior to Cycle 1 and at the end of Cycle 1.
- n. Pharmacodynamics (mRNA Transcript Levels). Optional samples to be collected on day 1 pre-MLN4924 (pevoneditstat) dose and on day 3 **OR** day 5 at 3 hours and 6 hours after the end of MLN4924 (pevoneditstat) infusion. See [Section 8.3](#) for details.
- o. Pharmacodynamics (NEDDylated Protein Analysis). Optional samples to be collected on day 1 pre-MLN4924 (pevoneditstat) dose, and at 10 hours and 24 hours after the end of MLN4924 (pevoneditstat) infusion. An additional sample is to be collected at the end of Cycle 1 on the same day as bone marrow evaluation. See [Section 8.4](#) for details.
- p. ALT, AST, Bilirubin. Prior to Cycle 1, prior to each dose of MLN4924 (pevoneditstat), and then weekly.

ADVL1712

THIS PROTOCOL IS FOR RESEARCH PURPOSES ONLY, SEE PAGE 1 FOR USAGE POLICY

q. Vital signs. Prior to each dose of MLN4924 (pevonodistat).

This listing only includes evaluations necessary to answer the primary and secondary aims. OBTAIN OTHER STUDIES AS REQUIRED FOR GOOD CLINICAL CARE.

Comments

(Include any held doses, or dose modifications)

Cycle 1

APPENDIX VIII-B: THERAPY DELIVERY MAP FOR CYCLE 2

Therapy Delivery Map – Cycle 2
 
This Therapy Delivery Map (TDM) relates to Cycle 2. Each cycle lasts 35 days.
	
Patient COG ID number _____
 
DOB _____

---	---

Criteria to start each cycle are listed in [Section 5.3](#). Extensive treatment details are in [Section 5.2](#).

This TDM is on 3 pages.

DRUG	ROUTE	DOSAGE	DAYS	IMPORTANT NOTES
IT Cytarabine (ARAC) (all patients)	Intrathecal (IT)	Age-based dosing: Age (yrs) Dose < 1 20 mg 1-1.99 30 mg 2-2.99 50 mg ≥ 3 70 mg	0	Given at the time of bone marrow aspirate/biopsy at the end of Cycle 1 OR on Day 0 of Cycle 2. See Section 5.2 and Section 5.3 for full details.
Azacitidine (AZA)	IV over 15 minutes	Age-based dosing: Age (yrs) Dose < 1 2.5 mg/kg/dose ≥ 1 75 mg/m ² /dose	1-5	On days 1, 3, and 5, administer before MLN4924 (pevoneditat) infusion. See timing below.
MLN4924 (Pevonedistat)	Intravenous (IV) over 1 hour	Patients < 1 year of age: Dose Level -1: 10 mg/m ² Dose Level 1: 15 mg/m ² Patients ≥ 1 year of age: Dose Level -1: 15 mg/m ² Dose Level 1: 20 mg/m ²	1, 3, 5	Administer 30-60 minutes after completion of azacitidine.
Fludarabine (FLU)	IV over 30 minutes	Age-based dosing: Age (yrs) Dose < 1 1 mg/kg/dose ≥ 1 30 mg/m ² /dose	6-10	

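### After Cycle 1, a 5–25% marrow that falls short of PR is told to proceed by 5.3 and is a removal criterion under 12.2.5C with 10.1a, and no readable text ranks the two

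*Combined protocol and SAP*

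**What the plan says.** **Going on to Cycle 2 (section 5.3).** The lead sentence lets patients continue "following completion of cycle 1 disease assessment if stable or greater response", subject to toxicity recovery. A later bullet covers a post-Cycle-1 marrow with blasts from 5% up to and including 25%: "then the patient should proceed to Cycle 2 of chemotherapy". The bullet does not mention PR.

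**Failure (12.2.5).** Item C is "M2 marrow that does not qualify for PR status", with no cycle attached. Item E, more than 25% blasts, is the only marrow item tied to the end of Cycle 1. Section 12.2.8 sets M2 at 5–25%. Under 12.2.4, PR needs an M2 marrow below 25% and a fall of at least half in the blast percentage.

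**Stopping (10.1).** The first criterion for removal from protocol therapy is "Evidence of treatment failure", with a reference to 12.2.5 and no exception. Section 5.2 uses the same failure section to stop treatment for persistent CNS disease: such patients "will be off study treatment and considered treatment failures".

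**Delivery maps (Appendices VIII-A and VIII-B).** Both point to 5.3: "Criteria to start each cycle are in" and "Criteria to start each cycle are listed in" that section.

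**The concern.** The 5.3 bullet and item C cover the same blast range and lead to opposite actions for any marrow in that range that is not a PR. A site working from the delivery map reads 5.3 and gives a second four-drug cycle. A site working from the removal criteria reads 10.1a and stops. Both are following the protocol.

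At stake is whether a child with residual leukemia receives a second intensive cycle. The composition of the Cycle 2 group would depend partly on which section a site consulted. That group feeds the descriptive summary of all toxicities in 11.3. The response description in 11.5 is also exposed, because a patient stopped after Cycle 1 has no Cycle 2 in which to reach remission.

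**Working it through.** The plan gives no figure to reproduce here, so the check applies the rules to each possible marrow result.

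**Inputs.** Let *b* be entry blasts (%) and *p* blasts after Cycle 1 (%), in an evaluable marrow.
- Proceed bullet (5.3): 5 ≤ *p* ≤ 25
- M2 (12.2.8): 5 ≤ *p* ≤ 25
- PR (12.2.4): 5 ≤ *p* < 25 and *p* ≤ *b*/2
- Failure item C (12.2.5): M2 and not PR
- Entry (4.1.2.1): relapse qualifies with 5% or more blasts, with 0.1% or more by flow cytometry, or on a cytogenetic or molecular abnormality. Low entry blasts are therefore possible.

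Both instructions apply when 5 ≤ *p* ≤ 25 and either *p* > *b*/2 or *p* = 25.

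**Worked case.** For 20% falling to 15%, the relative fall is (20 − 15)/20 = 25%, short of 50%, so it is not a PR. It is M2, so it is failure under item C and a removal criterion under 10.1a. It also lies within 5–25%, so 5.3 says proceed.

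**Whole-percent results from 5 to 25 (21 values), by entry blasts:**

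| Entry blasts | Highest PR value | Results with both instructions | Count |
|---|---|---|---|
| under 10% | none (*b*/2 < 5) | 5–25 | 21 of 21 |
| 10% | 5 | 6–25 | 20 of 21 |
| 20% | 10 | 11–25 | 15 of 21 |
| 30% | 15 | 16–25 | 10 of 21 |
| 40% | 20 | 21–25 | 5 of 21 |
| 50% or more | 24 | 25 only | 1 of 21 |

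The last row arises because M2 and the 5.3 bullet include 25% and PR does not. These counts are of possible values and carry no probability.

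**Search for a tie-breaker.**
- The lead sentence of 5.3 depends on a stable response, a category that 12.2 does not define.
- The delivery maps refer to 5.3 but do not say that it overrides 10.1a.
- Section 12.2.4 allows a discretionary repeat marrow to separate PR from regeneration. That may change a reading but does not settle a confirmed non-PR.
- Section 10.1f allows removal on the physician's judgment and does not reconcile the two rules.
- The design schema is not shown in the text available, so it could not be checked.

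**The case against.** The strongest reply is that the readable text leans one way. Section 5.3 is the specific rule: it names the marrow range and the action, whereas 10.1a is a one-line cross-reference. Both delivery maps send sites to 5.3. Item E, the one marrow item tied to Cycle 1, uses the same 25% cut as 5.3. The 'stable' condition has almost no content if item C removes patients. M3 would be failure E, M2 would be PR or failure C, and M1 would be remission or failure D, apart from M1 with persistent extramedullary disease. Where section 5 wants a failure to stop treatment, as for CNS disease, it says so at that point, and for a 5–25% marrow it says proceed.

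All of this stands as evidence of intent. It does not amount to a stated precedence: item C has no timepoint, 10.1a cites 12.2.5 whole, and the CNS rule shows that a 12.2.5 failure can end treatment.

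A reader might also infer that 5.3 sends clear progression on to Cycle 2, for example 1% rising to 22%. That rise of 21 points meets item A, "An increase in the extent of bone marrow infiltration by leukemic cells" by 20% or more (read here as percentage points), yet lies within the bullet's range. The documents do not support that reading. The bullet sits under the lead sentence, and such a rise is not stable on any ordinary meaning. The word is undefined, but the condition is there.

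**Conclusion.** The conflict is real on the face of the current text and should be corrected. It covers every 5–25% result when entry blasts are under 10%, narrows as entry blasts rise, and shrinks to the single value of 25% at 50% or above.

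The consequences are limited. The DLT window is Cycle 1 (5.6), so the MTD/RP2D decision is unaffected. The response analyses are descriptive, and 12.2.4 keeps PR out of the response calculation. What can shift is who receives Cycle 2, the Cycle 2 toxicity summary and the descriptive response summary. The entry blast distribution is not given, so neither a frequency nor an effect on any rate can be stated.

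A reader might go further and conclude that nothing in the protocol settles the matter. That is too strong: the schema cannot be read, and the indirect evidence favours proceeding. The supportable conclusion is that no readable text says 5.3 overrides 10.1a. It rests on literal reading of the sections and on evaluable marrows.

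**What to change.** **If these patients are meant to proceed, as seems likely:**
- In 10.1a (or item C), state that after Cycle 1 item C alone does not remove a patient, who may proceed under 5.3, while items A, B, D, E and F do remove. Keep item C only as a response label. It is not needed as a removal rule after Cycle 2, because 10.1e already ends therapy once two cycles are complete.
- In 5.3, replace the undefined 'stable' with a condition that none of 12.2.5 items A, B, D, E or F is met. With this wording, a rise of less than 20 points ending at or below 25% (for example 6% to 24%, a rise of 18) would go on to Cycle 2. The sponsor should confirm that this is acceptable.

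**If removal is intended instead:** limit the 5.3 bullet to marrows that meet PR. Patients entering with under 10% blasts could then never qualify through that bullet.

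Either route costs amendment wording only, with no added patients, samples or procedures.

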12.2.6 Relapse

Morphologic relapse after CR/CRp/CRi is defined as a reappearance of leukemic blasts in the peripheral blood or $\geq 5\%$ blasts in the bone marrow not attributable to any other cause (e.g. bone marrow regeneration after therapy). In the setting of recent treatment, if there are no circulating blasts and the bone marrow contains 5-20% blasts, a repeat bone marrow performed at least a week later is necessary to distinguish relapse from bone marrow regeneration. Should flow cytometric or molecular analyses suggest relapse (by reappearance of similar immunophenotype or mutation to the original leukemia) in the presence of $< 5\%$ blasts or $\geq 5\%$ blasts in a regenerating marrow, a repeat bone marrow performed at least a week later is necessary to confirm relapse by morphologic methods. In such instances, the date of recurrence is defined as the first date that more than 5% blasts were observed in the bone marrow. The reappearance or development of cytogenetically proven extramedullary disease also indicates relapse. Molecular and/or genetic relapse is characterized by reappearance of a cytogenetic or molecular abnormality.

12.2.7 Unevaluable:

Aplastic or severely hypocellular marrow. In this instance, marrow evaluation should be repeated weekly until response determination can be made through at least Day 60.

12.2.8 Bone Marrow Classification:

- M1 is $< 5\%$ blasts
- M2 is 5-25% blasts
- M3 is $> 25\%$ blasts

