12.2 Response Criteria for Patients with Leukemia

12.2.1 Complete Remission (CR)

Attainment of an M1 bone marrow (< 5% blasts and adequate marrow cellularity) with no evidence of circulating blasts or extramedullary disease and with recovery of peripheral blood counts (ANC \geq 1000/uL and platelet count \geq 100,000/uL). Flow cytometry may be useful to distinguish between leukemia and a regenerating bone marrow. There is no requirement for bone marrow cellularity.

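### The response rules contradict themselves for a hypocellular or unevaluable marrow after Cycle 1, so the same patient can be a remission or unevaluable

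*Combined protocol and SAP*

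**What the plan says.** **Timing and repeats (Section 5.3, Criteria for Starting Cycle 2).** The plan states: "Patients will have disease assessment on Day 36-39 of Cycle 1". After a dry tap or an aspirate without spicules, "a follow-up bone marrow aspirate and biopsy must be performed within 2 weeks to assess cellularity and response". For a hypocellular marrow, set at under 10% cellularity on biopsy, sites are to "continue to repeat bone marrow aspirate and/or biopsy not less than once every 14 days until response can be assessed". No end day is given. The next rule is a waiver: if counts recover within 14 days of an unevaluable marrow, "there is no need to repeat the marrow to confirm response". Section 5.3 gives no threshold for count recovery.

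**Unevaluable category (Section 12.2.7).** This covers an aplastic or severely hypocellular marrow, with no cut-off. The instruction is that "marrow evaluation should be repeated weekly until response determination can be made through at least Day 60". There is no exception for count recovery.

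**Remission categories (Sections 12.2.1 to 12.2.3).** CR, CRp and CRi all require an M1 marrow, which Section 12.2.8 defines by blasts under 5% alone. Section 12.2.1 adds adequate cellularity in its first sentence and closes with "There is no requirement for bone marrow cellularity". Sections 12.2.2 and 12.2.3 do not mention cellularity.

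**Use of the category.** Under Section 5.3, CR, CRp or CRi after Cycle 1 allows Cycle 2. Section 11.5 reports response descriptively, and Section 12.2.4 leaves PR out of the response calculation.

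**The concern.** The boundary between remission and unevaluable is set by rules that disagree. With PR excluded, the CR/CRp/CRi boundary largely fixes the reported response rate, and response is the trial's only secondary aim.

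The situation is not remote. Section 2.1 cites an earlier trial with median platelet and ANC recovery at 38 and 37 days and treats fludarabine and cytarabine as comparable in intensity. The first marrow here is due on Day 36–39, so some patients may be assessed at or before count recovery. The documents do not say how often the marrow will be hypocellular.

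Two things are at stake. One is a response figure that depends on which section was followed, or that can be settled after the result is known. The other is inconsistent response-based entry to Cycle 2.

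**Working it through.** The plan gives no response rate, target or power for this aim, so there is no figure to reproduce. The check compares the rules and then counts days and points.

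**1. Conditions side by side**

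| Category | Blasts | Cellularity | Counts |
|---|---|---|---|
| CR (12.2.1) | M1, <5% | required, then disclaimed | ANC ≥1000/µL and platelets ≥100,000/µL |
| CRp (12.2.2) | M1, <5% | silent | ANC ≥1000/µL, no platelet transfusion for 1 week |
| CRi (12.2.3) | M1, <5% | silent | ANC <1000/µL, or platelets <100,000/µL without transfusion independence |
| PR (12.2.4) | M2, at least halved | adequate, e.g. ≥10% on biopsy | none |
| Unevaluable (12.2.7) | none stated | aplastic or severely hypocellular | none |

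The three remission categories also exclude circulating blasts and extramedullary disease.

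**2. Patient A: empty marrow, low counts.** Take an aplastic marrow on Day 36 with blasts under 5%, no circulating blasts, no extramedullary disease and ANC below 1000/µL. CR and CRp fail on counts. Every written condition for CRi is met. Section 12.2.7 calls the same marrow unevaluable.

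**3. Patient B: unevaluable marrow, then count recovery.** Take an unevaluable marrow on Day 36, with counts recovered by Day 36 + 14 = 50.
- Section 5.3 requires no repeat, and its wording treats response as confirmed.
- If the marrow was a dry tap, no blast percentage exists, so the M1 requirement of CR, CRp and CRi has not been shown.
- If it was aplastic, Section 12.2.7 holds that response is not yet determined and asks for weekly repeats regardless of counts.
- If it was aplastic with blasts under 5%, and counts reach the CR levels, the last sentence of Section 12.2.1 admits CR while the first sentence refuses it.

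**4. Repeat marrows by Day 60**

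| First marrow | Weekly (12.2.7) | At the 14-day limit (5.3) | Waiver (5.3) |
|---|---|---|---|
| Day 36 | 43, 50, 57: three | 50: one (next Day 64) | none |
| Day 39 | 46, 53, 60: three | 53: one (next Day 67) | none |

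The single repeat is the minimum that Section 5.3 permits. A marrow that becomes evaluable between visits is read 0 to 7 days later at the 14-day limit than on the weekly schedule. The mean delay is 4.1 to 4.7 days across first marrows on Day 36 to 39, assuming the change is equally likely on each day up to Day 60.

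**5. Size of one reclassification.** No response denominator is defined, so a range is needed. The shift is 100/n percentage points.
- n = 6 (one dose-level cohort): 100/6 = 16.7
- n = 18 (maximum for dose confirmation, Section 11.1): 100/18 = 5.6
- n = 23 (maximum anticipated enrollment): 100/23 = 4.3
- n = 38 (absolute maximum): 100/38 = 2.6

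**The case against.** **The intervals do not strictly conflict.** A reader might infer that Sections 5.3 and 12.2.7 prescribe incompatible schedules. They do not: "not less than once every 14 days until response can be assessed" most naturally sets a minimum frequency, and weekly repeats satisfy both sections. This stands. What remains is a mismatch, because a site working at the Section 5.3 minimum falls short of Section 12.2.7.

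**Section 5.3 defers to Section 12.2.** It governs entry to Cycle 2 and points to Section 12.2 for response definitions, so the waiver could be read as a procedural rule that leaves the M1 requirement intact. This is fair in part, and the waiver does not say that counts alone make a CR. But it speaks of confirming response, and after an unevaluable marrow with no repeat there is no accepted M1 result to apply the definitions to.

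**Cellularity is covered elsewhere.** Section 12.2.4 says that adequate cellularity is needed to determine response, with an example that matches the 10% cut-off in Section 5.3. Read with Section 12.2.7, this makes unevaluable the sensible answer for an empty marrow. That may well be the intent. The sentence sits under PR only, however, and does not remove the disclaimer in Section 12.2.1.

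**Not every empty marrow becomes a remission.** CR and CRp also need count recovery, so the exposure without it lies in CRi. This stands.

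**Later data may settle it.** Patients who go on to Cycle 2 have a further marrow at its end. This helps them, but it does not fix the post-Cycle 1 category or help those who stop.

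**Conclusion.** The point holds as two contradictions and one mismatch. Section 12.2.1 contradicts itself on cellularity; with Sections 12.2.2 and 12.2.3 silent, an empty marrow can be CRi and unevaluable at once. The Section 5.3 waiver removes the marrow evidence that all three remission categories require, and Section 12.2.7 has no matching exception. The repeat intervals should be aligned but can both be met.

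Each affected patient moves the response rate by 2.6 to 16.7 points, depending on a denominator that the plan leaves open. How many patients would be affected cannot be derived from the documents.

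A reader might infer that these rules inflate a rate that decides whether phase 2 goes ahead. The documents do not support that. Section 11.5 makes response descriptive and hypothesis-generating, no response threshold is stated, and Sections 2.1 and 2.5 link phase 2 to the study's results only in general terms. The DLT and RP2D rules in Sections 5.6 and 11.3 do not use the response category. The defect should be corrected because even a descriptive rate needs one definition.

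**What to change.** 1. **Section 12.2.1:** remove the contradiction on cellularity, and make Sections 12.2.1 to 12.2.3 consistent with Section 12.2.7. Align the two descriptions of a hypocellular marrow (under 10% in Section 5.3; severely hypocellular, without a cut-off, in Section 12.2.7).
2. **Sections 5.3 and 12.2.7:** reconcile the waiver, the repeat interval and the end day, and define count recovery. The choice of schedule belongs to the study team; this review does not make it.
3. **Section 11.5:** name the response denominator. Count CR, CRp or CRi only when an evaluable M1 marrow is documented. Report other patients without one as unevaluable and keep them in the denominator. Add a sensitivity listing of patients whose repeat was waived under Section 5.3, with their counts and any later marrow.

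**Cost.** Items 1 and 3 are wording and need no new procedure. Item 2 is also wording, but the schedule chosen could change the number of repeat marrows (three against a minimum of one by Day 60, or none under the waiver). The reported response rate may be lower, and a true responder whose repeat was waived would count as a non-responder in the main figure. The listing makes such cases visible.
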